1. SYNOPSIS

Study Title	Elucidating major impact factors for high MELD recipient outcomes after orthotopic liver transplantation in adults.
Trial Design	Retrospective cohort study.
Trial Participants	High MELD patients receiving a liver transplant.
Planned Sample Size and Trial Duration	Eligible patients that received a liver graft within the last 15 years.
Trial duration	Up to 15 years Follow up.
Data Collection Period	January 01, 2010 to December 31, 2025
Primary Objective	To identify main risk factors for long term survival of high Sodium medical Model for End-Stage Liver Disease (NaMELD) patients and long-term graft survival after liver transplantation, with the aim prevent and treat pivotal factors prior to transplantation.
Secondary Objectives	
To confirm the risk factors for other long and short-term complication in high NaMELD patients.
 
To investigate the combination of risk factors and NaMELD graduation over time.

Primary Endpoint	Patient survival after liver transplantation.
Secondary Endpoints	
Assessment of biochemical parameters of liver function in the recipient during the initial postoperative phase and during the Follow up.
 
ICU stay.
 
Reasons for graft loss, death and retransplantation.

2. BACKGROUND AND RATIONALE:

2.1 Liver Transplantation and Model for End-Stage Liver Disease

Liver transplantation (LT) represents an important curative option for end stage liver disease such as decompensated cirrhosis, which remains a major challenge for today's health care system. The Model for End-Stage Liver Disease (MELD) is a worldwide-established scoring system for the evaluation of the severity of liver disease in allocation processes. However, the interpretation of MELD in clinical practice, particularly with regard to prioritizing potential liver transplant recipients, has revealed some hazards. These include the adaptation of MELD based on patient's characteristics, e.g. the presence of hepatocellular carcinoma, kidney failure and cardiovascular disease (Freeman et al. 2002). In addition, the remaining paucity of organ donors contributes to a rising number of transplantations of high MELD recipients. This leads to the risk of impaired outcomes, especially considering the interaction of additional donor and recipient risk factors, such as extended cold preservation, kidney function and warm ischemia (Schlegel et al. 2017). For a certain patient cohort living donation might represent a feasible approach as reported previously for high MELD patients (Selzner et al. 2010). Overall, the interaction of donor and recipient characteristics on the outcomes after LT in high MELD patients remains a scarcely investigated field. Therefore, the identification of factors influencing patient's outcomes after orthotopic liver transplantation becomes increasingly important, especially in high MELD recipients.

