2.2 Aim of the Study

We will create a comprehensive database to address several questions regarding the selection and outcome of liver transplantation in high NaMeld recipients:

1. Is the change of NaMeld score (delta Meld) prior to liver transplantation predictive for post-transplant outcome?
2. What are the characteristics of futile liver transplants in high NaMeld patients (high NaMeld recipients that do well vs early death)
3. Is exceeding the NaMeld threshold of 30 predictive of poor outcome?
4. Do all NaMeld factors are of equal importance for the prediction of futile outcome in high Meld recipients?

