8. APPENDIX

8.1 Donor variables

Donor Variables	
Biographic Characteristics	Age
	Height
	Weight
	Gender
	Living Donation (1) / Heart beating donation (NDD) (2)/ Non heart beating donor (DCD)
	Cause of Death
	ICU stay

Laboratory values prior to LT and following LT	Sodium Level
	Bilirubin Level
	AST/ALT Level
	Creatinine Levels

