8.2 Recipient Variables

Recipient Variables		
Overall Characteristics	Date of transplant	
	Date of Death	
Biographic Characteristics	Date of Retransplant	
	Date of last clinical visit	
	Age at Transplant	
	Height	
	Weight	
	Gender	
	Etiology of liver Disease	
	Bilirubin; INR; Creatinine; Sodium at MELD	
	Timepoints	
	Creatinine	D1-7
		3 months
		D90
		6months
		yearly
	eGFR	D1-D7
		3 months
		6 months
		yearly
		D90
	INR	6months
		12months
		D7
		3 months
		D90
	AST	6months
		Yearly
		D1 – D7
		3 months
		6months
	ALT	yearly
		D1 – D7
		3 months
		6months
		yearly

	Bilirubin	D7
		3 months
		6months
		yearly
	Sodium	D7
		3 months
		6months
		Yearly
	Alkaline	D7
	phosphatase	3 months
		6months
		Yearly
	Graft Survival at 1, 3, 5, 10 yrs	
Patient Survival at 1, 3, 5, 10 yrs		
Post-transplant ICU Stay		
Readmission within 30 days (1=yes; 0=no)		
Retransplantation date		
Cause of Graft Loss		
Cause of Death		

Freeman, Richard B.; Wiesner, Russell H.; Harper, Ann; McDiarmid, Sue V.; Lake, Jack; Edwards, Erick et al. (2002): The new liver allocation system: moving toward evidence-based transplantation policy. In: Liver Transplantation 8 (9), S. 851–858. DOI: 10.1053/jlts.2002.35927.

Selzner, Markus; Kashfi, Arash; Cattral, Mark S.; Selzner, Nazia; McGilvray, Ian D.; Greig, Paul D. et al. (2010): Live donor liver transplantation in high MELD score recipients. In: Annals of surgery 251 (1), S. 153–157. DOI: 10.1097/SLA.0b013e3181bc9c6a.

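### Cold and warm ischemia are named in the rationale as risk factors for poor outcome, but neither is on the list of variables to be collected

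*Protocol*

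**What the plan says.** The Synopsis gives the primary objective as "To identify main risk factors for long term survival of high Sodium medical Model for End-Stage Liver Disease (NaMELD) patients", and extends it to graft survival. Section 2.2 promises breadth: "We will create a comprehensive database to address several questions".

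Section 2.1 gives the reason for looking. On transplanting more high MELD recipients it says: "This leads to the risk of impaired outcomes, especially considering the interaction of additional donor and recipient risk factors", and its examples are "such as extended cold preservation, kidney function and warm ischemia". It then describes the joint effect of donor and recipient characteristics as little studied, which is the gap the study sets out to fill.

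A separate, earlier sentence in section 2.1 concerns how MELD is interpreted when patients are prioritised: "These include the adaptation of MELD based on patient's characteristics, e.g. the presence of hepatocellular carcinoma, kidney failure and cardiovascular disease".

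Section 8 contains the only variable lists in the protocol. The nearest donor item to ischemia is donor type, "Living Donation (1) / Heart beating donation (NDD) (2)/ Non heart beating donor (DCD"). The nearest recipient item to carcinoma is "Etiology of liver Disease".

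**The concern.** A risk-factor study can find only the factors it records. Here the rationale gives three examples of what harms high MELD recipients, and the two that arise from preservation and surgery are missing from the extraction list. If extraction runs as listed, the study cannot say whether cold or warm ischemia is a main risk factor. Nor can it look at how either combines with a high NaMELD, although donor-recipient interaction is the stated motivation. The comparison of futile transplants with recipients who do well (question 2 in section 2.2) would lack the same two candidates.

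This is not a detail that can wait for a statistical analysis plan. That plan can choose covariates only from data that have been extracted, and the extraction list is in the protocol.

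**Working it through.** No arithmetic applies: the protocol states no sample size, event count or effect size on this point. The check sets each factor named in section 2.1 against the lists in 8.1 and 8.2.

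**What the lists contain**

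- Donor (8.1): age, height, weight, gender, donor type, cause of death, ICU stay, sodium, bilirubin, AST/ALT and creatinine.
- Recipient (8.2): dates of transplant, death, retransplant and last visit; age, height, weight, gender and etiology; the NaMELD components; follow-up laboratory values including creatinine and eGFR; graft and patient survival; ICU stay; readmission; causes of graft loss and death.

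**Factors that section 2.1 ties to impaired outcome**

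| Factor | In 8.1 or 8.2? |
|---|---|
| Kidney function | Yes: creatinine among the NaMELD components, then creatinine and eGFR after transplant |
| Extended cold preservation | No |
| Warm ischemia | No; donor type is a partial, categorical stand-in |

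Two of the three are absent.

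**How far the proxy reaches.** Donor type marks which donors had circulatory arrest before retrieval. It does not measure how long the donor warm period lasted, says nothing about warm ischemia while the graft is implanted, and does not measure cold preservation.

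**Factors that section 2.1 cites only for adapting MELD**

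| Factor | In 8.1 or 8.2? |
|---|---|
| Hepatocellular carcinoma | No item of its own; may be recorded under etiology, and could be missed when it accompanies another primary disease |
| Kidney failure | Yes, through creatinine and eGFR |
| Cardiovascular disease | No |

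The second table is kept apart because its sentence makes no claim about outcome after transplant.

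**The case against.** Several points on the other side carry weight.

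- **The list is not declared exhaustive.** Section 5 says that data come from the hospital database and does not limit extraction to section 8. This stands against saying flatly that the study cannot examine ischemia; the supported statement is that it cannot with the variables listed. But section 8 is the only list given and goes down to individual time points and field coding, so it reads as the extraction specification. If the database already holds these times, listing them is cheap.
- **The objective looks to factors that can be dealt with before transplantation.** Ischemia arises around procurement and surgery and fits that aim less directly. This stands in part. Yet 8.1 already collects donor age and cause of death, which cannot be treated either, and section 2.1 names ischemia itself.
- **Most questions in section 2.2 are about prediction.** An unadjusted association can answer whether a NaMELD above 30 predicts poor outcome. This stands: the loss here is mainly an incomplete set of candidate risk factors.
- **Carcinoma and cardiovascular disease.** A reader might infer that the rationale calls these drivers of outcome as well. It does not; "the presence of hepatocellular carcinoma, kidney failure and cardiovascular disease" illustrates why MELD is adapted in prioritisation. They may be sensible covariates, but their absence does not contradict the rationale.
- **A shift in the NaMELD hazard ratio.** A reader might also infer a bias of known size and direction. The documents do not support one. Suppose long cold ischemia had a hazard ratio of 1.5 and occurred in 40% of high and 20% of lower NaMELD recipients (all assumed). The approximate bias factor is (1 + 0.5 × 0.40)/(1 + 0.5 × 0.20) = 1.20/1.10 = 1.09. With the two prevalences swapped it is 1.10/1.20 = 0.92, and with equal prevalences 1.00. The direction depends entirely on the assumption.

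**Conclusion.** The point holds in a narrow form. The protocol names cold preservation, kidney function and warm ischemia as risk factors for impaired outcome, sets out to identify the main risk factors, and lists variables for only one of the three. The size of the gap is two of three named factors; no size of bias can be given.

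This rests on reading section 8 as the list that will govern extraction. If the hospital database supplies ischemia times anyway, the defect is one of documentation, and the same edit cures it. The point does not extend to carcinoma or cardiovascular disease as named outcome factors, nor to the choice of covariate model or interaction test, which is commonly left to the statistical analysis plan. The change should be made because it bears directly on the primary objective and costs little.

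**What to change.** Before extraction, add cold ischemia time and warm ischemia time, both in minutes, to the section 8 list. Define the warm interval, since section 2.1 does not say whether it means the donor or the implantation period. Include both times among the candidate risk factors for patient and graft survival. If the sponsor prefers not to collect them, the protocol should explain why the risk-factor analysis can do without them.

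Optionally, add to 8.2 hepatocellular carcinoma at transplant (yes/no, separate from etiology) and cardiovascular disease (yes/no).

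The cost is two extra fields, or four with the optional items, in a retrospective extraction, plus an update to the data dictionary. The downside is abstraction time and some missing values in older cases. Adding the fields now avoids a second pass through the records from 2010 to 2025.

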2.2 Aim of the Study

We will create a comprehensive database to address several questions regarding the selection and outcome of liver transplantation in high NaMeld recipients:

1. Is the change of NaMeld score (delta Meld) prior to liver transplantation predictive for post-transplant outcome?
2. What are the characteristics of futile liver transplants in high NaMeld patients (high NaMeld recipients that do well vs early death)
3. Is exceeding the NaMeld threshold of 30 predictive of poor outcome?
4. Do all NaMeld factors are of equal importance for the prediction of futile outcome in high Meld recipients?

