4.2.2. Exclusion Criteria

- Patients undergo transplantation of organ(s) in addition to the liver.
- Patients who are enrolled in clinical trials of other unlicensed therapy.
- Patients younger than 18 years
- Patients for retransplant

5. Data Collection Procedure:

Data from January 01, 2010 to December 31, 2025 will be collected from hospital specific database. The collected data will be identified by unique study identifier only. Data will be stored for ten years after study completion in accordance with requirements of the corresponding ethic committees; publication or data source file stored will not contain any personal identifiers.

6. Data Analyses:

All statistical data will be generated by using JMP 13 (SAS Institute, Cary, NC), SPSS 22 statistical package (IBM, Chicago, IL, USA), or R (The R Foundation for Statistical Computing, Vienna, Austria). The main outcome measure will be the incidence of patient survival among different groups. Cumulative overall rejection-free rates will be calculated by Kaplan-Meier methods and differences between curves will be evaluated with the log-rank test and Bonferroni or Holm's correction. Continuous variable data will be analyzed nonparametrically using the Wilcoxon / Kruskal-Wallis' correction.

Categorical variables will be summarized as counts and proportions and compared by Chi squared test or Fisher's exact test as appropriate. These results will be represented as Odd's ratio or Hazard ratio with 95% confidence interval (CI). $P < 0.05$ will be considered statistically significant.

7. Ethical Consideration:

This protocol was approved by the local ethic committees of participating centers. No study activities will begin until approval is obtained. A waiver of informed consent is requested for this study since it meets the requirements for the common rule. Namely, it would be impractical to attempt to obtain consent for this study since many of these patients may now be deceased and/or lost to follow-up. Further, the exclusion of any patients would impact the quality of the study data. Finally, the study involves minimal risk to participants, as no change to patient care is taking place.

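### Section 2.2 asks whether NaMELD measures predict outcome, but Section 6 plans only measures of association, so a weak marker could be called predictive once the cohort is large enough

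*Protocol*

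**What the plan says.** Protocol Section 2.2 lists four questions about selection and outcome in high-NaMELD recipients. Three use the language of prediction:

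- Question 1: "Is the change of NaMeld score (delta Meld) prior to liver transplantation predictive for post-transplant outcome"
- Question 3: "Is exceeding the NaMeld threshold of 30 predictive of poor outcome"
- Question 4: "Do all NaMeld factors are of equal importance for the prediction of futile outcome in high Meld recipients"

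Section 6 (Data Analyses) sets out the methods. On the main outcome it says: "The main outcome measure will be the incidence of patient survival among different groups". For Kaplan-Meier curves, in a sentence written for rejection-free rates, "differences between curves will be evaluated with the log-rank test and Bonferroni or Holm's correction". Continuous variables are compared by Wilcoxon or Kruskal-Wallis tests. For the rest, "Categorical variables will be summarized as counts and proportions and compared by Chi squared test or Fisher's exact test as appropriate". On reporting, "These results will be represented as Odd's ratio or Hazard ratio with 95% confidence interval (CI". Significance is set at P below 0.05.

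The protocol names no measure of discrimination, calibration or predictive value, and gives no criterion for calling a marker predictive.

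**The concern.** A test of difference with an odds or hazard ratio shows that risk differs between groups on average. Whether a marker predicts is a separate question: how well does it sort individual recipients into those who will and will not have the outcome? A marker can pass the first test comfortably and do poorly on the second. For a fixed true effect the P value shrinks as patients are added, while discrimination does not change.

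This matters because Section 2.2 ties the questions to recipient selection and to describing futile transplants. If significance is the only criterion available when the results are written up, a marker that barely separates the two groups could be described as predictive of futility. Question 4 has a related gap: a separate significance test for each NaMELD component does not show how much each contributes to prediction.

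**Working it through.** **Inputs.** The protocol gives no sample size, event count, event rate or share of recipients above 30, so there is no stated figure to reproduce. From Section 6 come the 0.05 level (two-sided assumed) and the effect measures. Everything else below is assumed and varied.

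**Step 1: one worked case.** Assume 30% of recipients are above NaMELD 30, with early death of 10% above and 5% below.

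- Overall risk = 0.30 × 0.10 + 0.70 × 0.05 = 0.065
- Odds ratio = (0.10/0.90) / (0.05/0.95) = 2.11
- Sensitivity = 0.030/0.065 = 46%
- Specificity = (0.70 × 0.95)/0.935 = 71%
- AUC of a binary marker = (sensitivity + specificity)/2 = 0.59
- z = (0.10 − 0.05) / √[0.065 × 0.935 × (1/n₁ + 1/n₀)]

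| N | n₁ / n₀ | z | P | AUC |
|---|---|---|---|---|
| 500 | 150 / 350 | 2.08 | 0.04 | 0.59 |
| 1000 | 300 / 700 | 2.94 | 0.003 | 0.59 |
| 1500 | 450 / 1050 | 3.60 | 0.0003 | 0.59 |

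P falls with N and the AUC does not move.

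**Step 2: range over event rate and effect size.** Assume 20% flagged. Risk above the cut is p₁ = o/(1 + o), with o = OR × p₀/(1 − p₀). The share of flagged recipients without the event is 1 − p₁.

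| Baseline risk p₀ | Flagged without event, OR 1.5 / 2 / 3 | AUC, OR 1.5 / 2 / 3 |
|---|---|---|
| 3% | 96% / 94% / 92% | 0.54 / 0.57 / 0.61 |
| 5% | 93% / 91% / 86% | 0.54 / 0.57 / 0.61 |
| 10% | 86% / 82% / 75% | 0.54 / 0.56 / 0.61 |
| 20% | 73% / 67% / 57% | 0.53 / 0.56 / 0.60 |
| 30% | 61% / 54% / 44% | 0.53 / 0.56 / 0.59 |

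The share of flagged recipients without the event depends heavily on how common the outcome is. The weak discrimination does not.

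**Step 3: chance of reaching significance.** With 10% versus 5% and 20% flagged, power is 47%, 72%, 86% and 93% at N = 500, 1000, 1500 and 2000. About 1250 patients give 80% power. Significance is therefore possible but not assured in a small cohort.

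**Step 4: a continuous marker such as delta MELD.** The hazard ratio per standard deviation that just reaches P = 0.05 is exp(1.96/√deaths). With 150, 300 and 600 deaths this is 1.17, 1.12 and 1.08. Averaging pairwise concordance over a normally distributed marker gives C-statistics of about 0.54, 0.53 and 0.52.

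**The case against.** The strongest reply is that Section 6 never says a significant marker will be called predictive; it only says what counts as statistically significant. The Synopsis frames the primary objective as finding risk factors, and in clinical writing 'predictive' often means no more than prognostically associated. On that reading, hazard ratios with confidence intervals are the natural output. This stands in part, and it is why rewording the questions is an acceptable remedy. It does not remove the mismatch, because Section 2.2 uses the word in the context of selection and futility.

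A second reply is that C-statistics, calibration and optimism correction are details usually left to a statistical analysis plan, which is not at hand. That is fair as to detail, so their absence alone is not the point. The point is that the tests and effect measures the protocol does name all measure association.

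Three stronger readings are tempting and are not supported:

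- *A reader might infer that Section 6 gives no absolute risks.* It plans counts, proportions and Kaplan-Meier rates, and Appendix 8.2 lists patient survival at 1, 3, 5 and 10 years. A two-by-two table from these data would also yield sensitivity and specificity. They are simply not named or made a criterion.
- *A reader might infer that a marker wrong for about nine in ten flagged recipients would be reported as predictive.* That share needs a rare outcome such as early death. Question 3 gives no time point, and the primary objective is long-term survival. Positive predictive value is also limited by the event rate, so a low value does not by itself show a flawed analysis. And Step 3 supports 'could', not 'would'.
- *A reader might count question 4 as asking whether a marker predicts.* It asks about the relative importance of the components.

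**Conclusion.** The point holds as a mismatch between question and method. Questions 1 and 3 ask whether a marker predicts, question 4 asks about component importance for prediction, and Section 6 as written answers none of these. The size rests wholly on assumed inputs. Across baseline risks of 3% to 30% and odds ratios of 1.5 to 3 with 20% flagged, the AUC is 0.53 to 0.61, including cases that are readily significant in a large cohort. That is the robust part. The share of flagged recipients without the event, 96% down to 44%, varies too much with the outcome definition to be quoted as a single figure.

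**What to change.** Add to Section 6 that 'predictive' will be judged by predictive accuracy at a stated time point:

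- **NaMELD above 30:** sensitivity, specificity, positive predictive value and absolute risk, each with a 95% confidence interval.
- **NaMELD and delta MELD:** C-statistic or time-dependent AUC with a 95% confidence interval, including the gain from adding delta MELD to NaMELD at transplant.
- **Any fitted multi-component model (question 4):** the same, plus calibration and bootstrap optimism correction, since the model would be fitted and judged on the same patients.
- **Odds and hazard ratios:** keep them, labelled as measures of association.

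Alternatively, reword questions 1, 3 and 4 as questions of association and leave Section 6 as it is on this point.

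The cost is a few lines of text and a little more analysis. Transplant and death dates and the NaMELD components are already listed in Appendix 8.2, so no new data are needed. The downside is that a statistically significant marker may have to be reported as poorly predictive.

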4.2.1. Inclusion Criteria

- Patient registered for liver transplantation.
- Patients at least 18 years of age

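### Aim 4 asks whether the NaMELD components matter equally in high-NaMELD recipients, but the one-variable tests named in section 6 cannot test equality and can be distorted by selection on the score

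*Protocol*

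**What the plan says.** The fourth question in section 2.2 is "Do all NaMeld factors are of equal importance for the prediction of futile outcome in high Meld recipients". It compares the parts of a score among patients chosen for a high value of that score. The synopsis describes the participants in the same way: "High MELD patients receiving a liver transplant".

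Section 6 (Data Analyses) names the tools:
- continuous data: "Continuous variable data will be analyzed nonparametrically using the Wilcoxon / Kruskal-Wallis' correction"
- survival curves: "differences between curves will be evaluated with the log-rank test and Bonferroni or Holm's correction"
- categorical data: "compared by Chi squared test or Fisher's exact test as appropriate"

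Odds ratios or hazard ratios with 95% intervals are promised, but no regression model and no covariates are named. Appendix 8.2 lists all four components for collection: "Bilirubin; INR; Creatinine; Sodium at MELD".

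Two things are left open. The only cut-off given is 30, and it belongs to a different question in section 2.2: "Is exceeding the NaMeld threshold of 30 predictive of poor outcome". The inclusion criteria set no score limit; apart from age, the only requirement is "Patient registered for liver transplantation".

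**The concern.** There are two separate problems.

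**Equality is never tested.** A rank test on bilirubin asks whether bilirubin is related to outcome. Four such tests answer four questions of that kind. None asks whether the four effects are the same, which is what Aim 4 asks. A Bonferroni or Holm adjustment changes the thresholds but not the hypotheses. If some components reach P < 0.05 and others do not, the natural reading is that they differ in importance, and chance alone often produces that pattern.

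**Selection changes the relation between components.** Among patients with a high total, a low value on one component tends to be offset by high values on the others. Conditioning on the sum therefore lowers the correlations between components and can make them negative. A one-variable test of one component then picks up part of the others' effects.

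At stake is one of the four stated questions, not the survival endpoint. The reported ranking of components could be an artefact of the method.

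**Working it through.** The protocol states no sample size, event count or effect size, so there is no figure of its own to reproduce. All numerical inputs below are assumptions.

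**Set-up.** Four standardised normal components, coded so that higher means a higher score; score = their sum; common pairwise correlation ρ before selection; top fraction of the score selected; early death from a logistic model.

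**1. Do separate tests answer an equality question?** Equality is β1 = β2 = β3 = β4, which is 4 − 1 = 3 contrasts. If each separate test had power p and the tests were independent, the chance of a mixed verdict would be 1 − p⁴ − (1 − p)⁴. At p = 0.5 this is 1 − 0.0625 − 0.0625 = 0.875, although all effects are equal.

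Simulation with dependent tests: true OR 1.40 per SD for all four, top 30% selected, about 13% events, two-sided 0.05, 1000 replicates.

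| ρ | mixed verdict, n = 300 | mixed verdict, n = 600 |
|---|---|---|
| 0 | 34% | 49% |
| 0.2 | 60% | 86% |
| 0.4 | 79% | 80% |
| 0.6 | 71% | 34% |

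The joint logistic model with a 3-df test rejected in 4% to 6% throughout. The share of mixed verdicts depends on power. I repeated the simulation with 25% events (2000 replicates). Mixed verdicts ran from 41% to 87% at n = 300 and from 13% to 92% at n = 600. The 13% is at ρ = 0.6, where usually all four tests are significant. The 3-df test again rejected in 4% to 5%.

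**2. What does selection do to the correlation?** For the top 30%, z = 0.524, λ = φ(z)/0.30 = 1.159 and δ = λ(λ − z) = 0.7355. With c = (1 + 3ρ)/4, the within-stratum correlation is (ρ − cδ)/(1 − cδ).
- ρ = 0: c = 0.25, cδ = 0.184; −0.184/0.816 = −0.23
- ρ = 0.4: c = 0.55, cδ = 0.4045; −0.0045/0.5955 = −0.01
- ρ = 0.6: c = 0.70, cδ = 0.515; 0.085/0.485 = +0.18

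It is zero at ρ = (δ/4)/(1 − 3δ/4) = 0.184/0.448 = 0.41. Simulated values agree to within 0.01.

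**3. What do one-variable odds ratios show in the top 30%?** Values are per SD; the true OR is 2.0 for a harmful component in the first two scenarios, 1.0 for an inert one, and 1.5 in the last column.

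| ρ | one harmful: harmful / inert | two harmful: harmful / inert | four equal |
|---|---|---|---|
| 0 | 2.02 / 0.85–0.87 | 1.67 / 0.75 | 1.14–1.16 |
| 0.2 | 1.97 / 0.92–0.93 | 1.76–1.80 / 0.85–0.86 | 1.27–1.29 |
| 0.4 | 1.99 / 1.00–1.01 | 1.93 / 1.01–1.02 | 1.45–1.48 |
| 0.6 | 2.00 / 1.15–1.16 | not run | not run |

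The cut matters too. At ρ = 0.4 with one harmful component, the inert ones show 1.07 for the top 50% and 0.95–0.96 for the top 15%.

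With one harmful component, a Wilcoxon test called an inert one significantly protective in 13% (n = 300) and 24% (n = 600) of studies at ρ = 0, in 7% and 9% at ρ = 0.2, and in 3% and 2% at ρ = 0.4. The nominal rate in that direction is 2.5%.

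**4. Does a joint model cure it?** With all four components in one logistic model, fitted in the selected patients only, inert components gave 0.98–1.02, a true 2.0 gave 1.97–2.03 and a true 1.5 gave 1.47–1.52.

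**The case against.** **The analysis plan may supply the model.** Section 6 is a general list and does not assign the rank tests to Aim 4. It promises odds and hazard ratios, which a rank test does not yield, and the synopsis has an objective on risk factors in combination. A separate analysis plan could name a joint model. This is fair, and it is why the point rests only on what section 6 states. But section 6 does fix a method for continuous variables, the components are continuous, and that method does not answer the question posed.

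**Equal effects may still look equal.** With equal score weights, four equal odds ratios shrink together, and a lone harmful component still stands out. That holds for average estimates. It does not rescue a verdict read from separate P-values in a few hundred patients (step 1). With unequal weights of 1, 1.5, 1 and 0.5, four equal odds ratios of 1.40 appeared as 1.04 to 1.26 at ρ = 0 and as 1.36 to 1.50 at ρ = 0.4, so they need not even look equal.

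**The one-variable result is a true description.** Within the selected group it is. What it distorts is the comparison of importance between components.

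**A stronger reading is tempting.** A reader might infer that selecting on a high score always forces the components into negative correlation, so that harmful ones must look weak and inert ones must look protective. The documents do not support this. They give no correlations. The effect on inert components vanishes near ρ = 0.4 at a top-30% cut and reverses at 0.6, and a lone harmful component was not weakened in any scenario. Nor may one assume that 30 is the cut-off for Aim 4, since it appears only in the threshold question.

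**Conclusion.** The point holds in two parts of different strength.

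The firm part is that separate one-variable tests do not test whether four effects are equal, whatever the correlation. How often this misleads depends on assumed effect size, event rate, correlation and sample size. With 300 patients and about 13% events, four truly equal components gave a mixed verdict in 34% to 79% of simulated studies. Where power is high enough for all four to be significant, the share falls.

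The conditional part is that selection on the score can distort one-variable comparisons. With ρ of about 0 to 0.3, harmful components can look weaker when two or more matter, and inert ones can look protective. Direction and size cannot be settled from the protocol, because it gives neither the correlations nor the Aim 4 cut-off.

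The sponsor should correct this. It affects one of four stated questions and leaves the primary survival endpoint untouched.

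**What to change.** State in section 6 that Aim 4 will be answered by one model in high-NaMELD recipients: logistic for early death or Cox for survival. It should hold bilirubin, INR and creatinine (log scale) and sodium together, with sodium coded in the same direction as the others. Pre-state the common scale, for example per SD or relative to each component's weight in the score. Test equality of the four effects with a single 3-df test, and report the four estimates with intervals. State the NaMELD cut-off that defines the Aim 4 group. One-variable results may stay as description.

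A model in all recipients with component-by-high-NaMELD interactions is optional. It is not needed to remove the distortion, because the joint model in the selected patients already recovered the true values.

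The cost is about a paragraph of text, a little more analysis work and a choice of scale that must be defended. All four components are already on the data list.
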